6.1 OVERVIEW OF STUDY DESIGN

This study is a fixed-dose, randomized, two-arm Phase 3 trial to assess the efficacy and safety of ublituximab in combination with ibrutinib compared to ibrutinib alone in patients with CLL who have received at least one prior standard treatment regimen and who have at least one high-risk cytogenetic abnormality (17p deletion, 11q deletion, and/or P53 gene mutation).

Following screening, patients meeting the inclusion/exclusion criteria will be randomized in a 1:1 ratio, to either:

[figure not shown]
- Arm A: Ublituximab + ibrutinib; or
- Arm B: Ibrutinib

Randomized patients will be stratified according to prior lines of therapy (1 prior vs 2 or more prior lines of therapy).

All study patients will be evaluated for response after cycles 2, 4, and 6, then every 3 cycles thereafter if patient is on active treatment, or approximately every 3 months thereafter if patient is in follow up. The best clinical response as well as disease progression will be determined by an Independent Review Committee (IRC).

Patients will continue treatment until the occurrence of definitive disease progression, unacceptable toxicity, or withdrawal from the study due to investigator decision or other reasons. Patients who discontinue study treatment for reasons other than disease progression will continue to be followed for progression and/or survival approximately every 3 months.

Upon first assessment scan, or confirmation scan (if necessary), of the last randomized patient, and site submission of all required efficacy and safety data, the independent DSMB will review the primary and secondary efficacy analyses, and safety data.

6.2 REGISTRATION AND RANDOMIZATION

The patient must sign consent after being informed of the procedures to be followed, the experimental nature of the treatment, potential benefits, alternatives, side-effects, risks and

UTX-IB-301

discomforts. Patients who have signed informed consent and who are eligible will be randomized in a 1:1 ratio to Arm A (ublituximab plus ibrutinib) or Arm B (ibrutinib alone).

Investigators will use an interactive web response system (IWRS) which will assign patients to either treatment Arm A (ublituximab plus ibrutinib) or treatment Arm B (ibrutinib alone).

Patients should begin study treatment within 4 days of randomization. In case of administrative or other delays, every attempt should be made to initiate study drug as soon as possible but no more than 7 days from randomization. Please see the IWRS Manual for additional information on randomization.

Upon entering patient information into the IWRS, investigators will receive an enrollment approval and a unique patient identifier that will include the randomization assignment. This confirmation must be received by the site prior to dispensing study drug to the participant. Further details about the patient registration process using the IWRS system will be outlined in the IWRS Manual.

6.3 STUDY SITES

Up to 200 study sites may be asked to participate in this study. Enrollment is expected to be completed approximately 18-24 months after the first patient is randomized.

6.4 DISCONTINUATION FROM STUDY TREATMENT

Patients will be discontinued from study treatment for any of the following reasons:

- Disease progression
- Intolerable toxicity related to study drug
- Patient requests to withdraw consent or discontinue treatment
- Pregnancy
- Inability of the patient to comply with study requirements
- Conditions requiring therapeutic intervention not permitted by the protocol
- Non-compliance/lost to follow-up
- Investigator discretion
- Discontinuation of the study by the Sponsor

Patients who discontinue from study treatment (for reasons other than progressive disease) will continue to be followed for progression. **Every attempt to continue to follow the patient for progression should be made.**

After withdrawal from protocol treatment, patients should be followed for AEs for 30 calendar days after their last dose of either study drug. All new AEs occurring during this period must be reported and followed until resolution, unless, in the opinion of the investigator, these values are not likely to improve because of the underlying disease. In this case the investigators must record his or her reasoning for this decision in the patient's medical records and as a comment on the electronic Case Report Form (eCRF).

All patients who have CTCAE Grade 3 or 4 laboratory abnormalities at the time of withdrawal should be followed until the laboratory values have returned to Grade 1 or 2, unless in the opinion of the investigator, it is not likely that these values are to improve because of the underlying disease. In this

UTX-IB-301

case, the investigator must record his or her reasoning for making this decision in the patient's medical records and as a comment on the eCRF.

UTX-IB-301

7 STUDY ASSESSMENTS AND TREATMENT SCHEDULE

Table 2 below lists all of the required assessments that should be performed at each study visit.

TABLE 2: STUDY ASSESSMENTS AND TREATMENT SCHEDULE

	Screen Screen			пероі	Cycles 2-6 ² After Cycle 6 ³							
Cycle = 28 days	*	Cycle 1 ¹				C2	С3	C4	C5	C6	q3 Cycles (C9, 12, etc.)	End of
Procedure\Days	-21-0	D1	D24	D8	D15			Day 1			Day 1	study
Informed consent	X											
Medical history	X											
Rai Staging	X											
ECOG Performance Status	X	X				X	X	X	X	X	X	Х
Physical Examination	X	X				X	X	X	Х	Х	X	X
Vital signs (pulse, BP, temp)	х	X	х	X	Х	X	X	х	х	х	х	х
BM aspirate/biopsy ⁵	Х											
12-lead EKG	Х											
Tumor evaluation ⁶	х	After the completion of cycles 2, 4 and 6 then after the completion of every 3 cycles if under treatment or every 3 months if in follow up										
Serology: HCV, HBV, CMV ⁷	х											
MRD8						For patients in PR or CR at response assessment intervals beginning at the Cycle 6 response assessment						
Hematology ⁹	X	X	X	X	X	X	X	X	X	X	X	Х
Serum Chemistry ⁸	X	X		Х	X	X	X	X	X	Х	X	X
PT/INR	X					X		X				
Serum Pregnancy Test ¹⁰	X											
Urinalysis	X											
Quantitative Immunoglobulin ¹¹		X			X		X			X		
β ₂ -microglobulin	X											
FISH Analysis ¹²	X											
Concomitant Medications	X	X	X	X	X	X	X	X	X	X	X	X
Adverse Event Evaluation ¹⁵	х	X	х	х	х	Х	Х	Х	Х	х	х	х
Treatment Schedule												
Ublituximab Dose		X16	X	X	X	X	X	X	X	X	X	

 $^{^{1}}$ Physical Exam, Vital Signs, ECOG PS, Hematology and Serum Chemistry visit days have +/- 3 day window

² Physical Exam, Vital Signs, ECOG PS, Hematology and Serum Chemistry visit days have +/- 7 day window

³ Physical Exam, Vital Signs, ECOG PS, Hematology and Serum Chemistry visit days have +/- 14 day window

⁴ Day 2 visit only required for patients randomized into Arm A.

⁵ Unilateral bone marrow aspirate and/or biopsy performed at investigator discretion in patients for whom assessment of extent of CLL involvement and bone marrow cellularity is important in determining eligibility. In addition, a post-baseline bone marrow biopsy should be completed to confirm potential CR by radiological assessment.

⁶ Scans for screening should be completed within 30 days prior to Day 1 of Cycle 1. Response tumor evaluations have a +/- 7 day window. Radiology assessment should include CT or MRI imaging of neck, chest, abdomen, and pelvis.

⁷ Serum virology to include HBsAg, HBc antibody and CMV. If HBcAg, HBc antibody, HCV or CMV is positive, patients must be evaluated for the presence of

⁸ Peripheral Blood sample draw (See study manual for all central lab instructions. +/- 7 day window for MRD sample). For patients MRD negative by peripheral blood, a bone marrow sample should be completed to confirm MRD negativity.

⁹ Must be obtained prior to ublituximab administration if on a day of infusion.

¹⁰ For women of child bearing potential, completed within 3 days prior to Day 1 of Cycle 1

¹² For del(13q), del(11q), del(17p), and (12)trisomy, IgHV and P53 gene mutation status in peripheral blood. Central FISH analysis can be performed on UTX-IB-301 study or the TGTX-LAB-001 screening protocol.

¹⁵ If clinically significant adverse event or abnormal result is observed that is not resolved by the end-of treatment visit, continue to monitor and record until stabilization or resolution of event

¹⁶ Patients should receive up to 150 mg on Day 1 and 750 mg on Day 2. Collect a hematology panel prior to Day 2/Cycle 1 infusion.

Ibrutinib Dose	Days 1 – 28 (Daily)	
*Randomize Days -7 to 0		

7.1 LABORATORY ASSESSMENTS

Laboratory assessments will be collected as specified in the study assessments and treatment schema. Please refer to the lab manual for instructions outlining collection and shipment procedures for assessments requiring central labs.

7.1.1 LOCAL LABORATORY ASSESSMENTS

1. Hematologic profile and serum chemistry to include:

Hematologic Profile						
Hematocrit	Neutrophils	Platelet count				
Hemoglobin	Lymphocytes					
Erythrocyte count	Monocytes					
Absolute neutrophil count	Eosinophils					
Absolute leukocyte count	Basophils					
Serum Chemistry						
Albumin	Creatinine	SGOT [AST]				
Alkaline phosphatase	Glucose	SGPT [ALT]				
Bicarbonate	LDH	Sodium				
BUN	Magnesium	Total bilirubin				
Calcium	Phosphorus	Total Protein				
Chloride	Potassium	Uric acid				

- 2. Serum β-HCG test.
- 3. Coagulation lab tests to include, PT, aPTT, and INR.
- 4. Quantitative immunoglobulin (IgG, IgM, IgA, IgE).
- 5. Urinalysis dipstick for pH, protein, glucose, blood, nitrite, leukocytes
- 6. Beta2-microglobulin
- 7. Serum Virology to include HBsAG, HBc antibody, HCV antibody, and CMV (PCR to rule out positive Hepatitis or CMV result as warranted)
- 8. Baseline bone marrow aspirate/biopsy (if applicable)

[figure not shown]
7.1.2 CENTRAL LABORATORY ASSESSMENTS

The following assessments will be shipped to and analyzed at a central laboratory. Please see Lab Manual for processing, handling, and shipping instructions.

- Fluorescence in situ hybridization (FISH) of peripheral blood for 13q deletion, 11q deletion, 17p deletion, trisomy 12, IgHV, and P53 gene mutation status. Central FISH analysis can be performed on UTX-IB-301 study or the TGTX-LAB-001 screening protocol.
- 2. Minimal Residual Disease (MRD) assessment for all patients in PR or CR at response assessment intervals beginning at the Cycle 6 response assessment.

UTX-IB-301

8.1 TREATMENT SUMMARY

Treatment will be administered on an outpatient basis in 4-week (28 day) cycles.

Patients randomized to Arm A will receive ublituximab and ibrutinib, while patients randomized to Arm B will receive ibrutinib alone. Treatment schema is outlined below.

Treatment Schema Overview

Cycle 1:

Arm A			Arm B	
Ublituximab		Ibrutinib	Ibrutinib	
Day 1	Day 2	Day 8 & 15	Daily	Daily
≤150mg	750 mg	900 mg	420 mg	420 mg

Cycles 2 through 6:

Arm A	Arm B	
Ublituximab	Ibrutinib	Ibrutinib
Day 1 Cycles 2, 3, 4, 5, 6	Daily	Daily
900 mg	420 mg	420 mg

Beyond Cycle 6:

Arm A	Arm B	
Ublituximab	Ibrutinib	Ibrutinib
Day 1 every 3 months thereafter (e.g. cycle 9, 12, etc)	Daily	Daily
900 mg	420 mg	420 mg

8.2 AGENT ADMINISTRATION

Ublituximab treatment will be administered as an IV infusion while ibrutinib will be administered orally, both on an outpatient basis.

8.2.1 GUIDELINES FOR ADMINISTRATION OF UBLITUXIMAB

- *Method of Administration:* Ublituximab will be administered as an intravenous infusion through a dedicated line.
- Potential Drug Interactions: No Drug Interactions have been reported to date.
- Pre-medications: Pre-medicate approximately 30 minutes prior to each dose of ublituximab
 with an antihistamine (diphenhydramine 50 mg or equivalent), and a corticosteroid
 (dexamethasone 10-20 mg or equivalent). Use of corticosteroids as a premedication after
 cycle 6 is at the discretion of the investigator.
 - Use of oral acetaminophen should be restricted to patients who experience fever or pyrexia after week 1 dose, or as clinically warranted.

UTX-IB-301

- *Hypersensitivity and Infusion Reaction Precautions*: Medication and resuscitation equipment must be available per institutional guidelines prior to ublituximab administration for the emergency management of potential anaphylactic reactions.
- Patient Care Implications:
 - o Ublituximab should not be administered as an IV push or bolus.
 - o Ublituximab should only be diluted in 0.9% NaCl.
 - Diluted ublituximab should be checked before administration for cloudiness, color, or deposits. Ublituximab should not be administered if does not conform to the specifications. Immediately inform the Monitor/Sponsor with any product quality concerns or questions.
 - o It is recommended that ublituximab be administered immediately after dilution.
 - No other treatment may be co-administered with ublituximab (other than for immediate intervention for adverse event).
 - o Concurrent glucocorticoid therapy as long as started for at least 7 days prior to study entry (≤ 10 mg per day of prednisone or equivalent) is allowed as clinically warranted.
 - Since infusion-related hypotension may occur, antihypertensive medications should be withheld 24 hours prior to and throughout infusion of ublituximab
 - For patients at risk for tumor lysis syndrome in the opinion of the treating investigator, prophylaxis with allopurinol or per recommended institutional standards should be considered.

8.2.1.1 INFUSION RELATED REACTIONS AND INFUSION RATE GUIDANCE - UBLITUXIMAB

Infusion related reactions, including severe reactions, have been reported with ublituximab administration in patients with CLL. Guidelines are provided below for patients who experience such reactions. Symptomatic infusion reactions, despite premedication, may be treated at the discretion of the treating physician, including but not limited to: oral acetaminophen 650 mg (or equivalent), corticosteroids, antihistamines, oxygen, and bronchodilators.

The following are recommended infusion rate reduction/delay guidelines for patients who experience severe Infusion Related Reactions (IRR's) in which treatment should be interrupted. Final decision for infusion rate reduction/delay or discontinuation resides with the treating investigator.

1st or 2nd Infusion Interruption:

- Hold infusion and closely monitored patient, institute symptomatic medical management until resolution of IRR symptoms.
- Following the judgment of the Investigator, and provided the patient is stable, the infusion may be resumed at no more than half the previous rate.
- If the patient does not experience any further IRR symptoms, infusion rate escalation may resume at the increments and intervals as appropriate at the treatment cycle dose (see Section 8.2.1.2).

UTX-IB-301

3rd Infusion Interruption (same day):

- Discontinue infusion for that day monitor patient for resolution of all symptoms. Patient should have all vital signs completed as well as any other standard of care procedures completed as warranted by the Investigator prior to release of patient from study site.
- Any remaining diluted investigational product should be discarded.

If the infusion discontinued is the Cycle, 1 Day 1 infusion, administer the scheduled Cycle 1, Day 2 dose of 750 mg according to the protocol dosing schedule.

8.2.1.2 FLOW RATE RECOMMENDATIONS FOR UBLITUXIMAB ADMINISTRATION

Cycle 1 Day 1 & 2 infusion over 4 hours

Cycle 1	Ublituximab	o Total volume Infus			ion rate	
	Dose	to be infused	T0 to T30'	T30' to T1H	T1H to T2H	T2H to T4H
Day 1	150 mg	250 mL	10 mL/H	20 mL/H	35 mL/H	100 mL/H
Day 2	750 mg	500 mL	10 mL/H	20 mL/H	85 mL/H	200 mL/H

Cycle 1 Day 8 & 15 infusions over 3 hours

Ublituximab Dose	Total volume to be		Infusion rate		
	infused	T0 to T1H	T1H to T2H	T2H to T3H	
900 mg	500 mL	50 mL/H	150 mL/H	300 mL/H	

Cycle 2 and remaining infusions over 90 minutes

Ublituximab Dose	Total volume to be	Infusion rate		
	infused	T0 to T30min	T30min to T90min	
900 mg	500 mL	200 mL/H	400 mL/H	

8.2.1.3 DISPENSING OF UBLITUXIMAB

Before dispensing, the site pharmacist or his/her representative must check that ublituximab is in accordance with the product specifications and the product is within the re-test date.

The exact dose and the date and time of administration of ublituximab must be recorded within the eCRF, patient's medical records, and/or in the drug accountability records.

The pharmacist or his/her representative should complete the accountability forms with information concerning the dispensation of ublituximab. Preparation should be done by the Pharmacist or his/her representative according to instructions for sterile dilution provided below.

The Pharmacist or his/her representative should record the date dispensed and patient's number and initials, as well as complete the accountability forms with information concerning the dispensation of ublituximab. Preparation should be done by the Pharmacist or his/her representative according to instructions for sterile dilution.

UTX-IB-301

8.2.1.3.1 DILUTIONS OF UBLITUXIMAB

Ublituximab should not be mixed with other medicinal products. Ublituximab should only be diluted in 0.9% NaCl before use.

Dilutions for Cycle 1 Day 1 & Day 2 Infusions

Dose of ublituximab for infusion

Cycle 1 Day 1: 150 mg Cycle 1 Day 2: 750 mg

Dilutions for ≥Cycle 1 Day 8 Infusions

Dose of ublituximab for infusion

900 mg

Dilutions for ≥Cycle 1 Day 8 Infusions

Dose of ublituximab for infusion

 $900 \, \mathrm{mg}$

8.2.2 GUIDELINES FOR ADMINISTRATION OF IBRUTINIB

Guidelines for the administration of ibrutinib are per the FDA approved prescribing information. Please refer to www.imbruvica.com for the most up to date information.

- *Method of Administration:* Ibrutinib will be administered orally once daily in accordance with prescribing information
- Potential Drug Interactions: Avoid co-administration with strong CYP3A inhibitors/inducers.
 If a moderate CYP3A inhibitor/inducers must be used, see ibrutinib prescribing information
 for dose reduction guidelines and further information. For this reason, patients requiring
 treatment with strong inhibitors of CYP3A are excluded from enrollment. Also avoid
 grapefruit and Seville oranges during treatment, as these contain moderate inhibitors of
 CYP3A and can alter ibrutinib pharmacokinetics. See Appendix D HEPATITIS B SEROLOGIC
 TEST RESULTS.
- Pre-medications: None

UTX-IB-301

Ibrutinib should be obtained via standard commercial channels. Ibrutinib should be self-administered (by the patient). Starting on Cycle 1 Day 1 the patient should maintain a daily diary recording the time and date of the administration of ibrutinib. Tablets should be taken at approximately the same time each day, except for days when the patient has a scheduled visit to the site. Patients should be instructed to swallow the tablets as a whole and should not chew or crush them. If a dose of ibrutinib is missed, it should be taken as soon as possible on the same day. If it is missed for the entire day, it should not be replaced. If vomiting occurs, no attempt should be made to replace the vomited dose.

Study drug compliance (i.e. the patient's daily diary) should be reviewed with the patient at the beginning of each new treatment cycle. Missed doses should be documented in the appropriate eCRF. Patients should record the dose of ibrutinib taken for each dose in a drug diary.

For patients having surgery, hold ibrutinib for at least 7 days prior to planned surgery and for 7 days following surgery.

8.3 CRITERIA FOR ONGOING TREATMENT

Continue treatment as per protocol provided that patient has:

- No intolerable toxicities related to study drug.
 - o Treatment may be delayed to recover from toxicity for a maximum of four weeks.
- No clinical or radiographic evidence of disease progression.
- Not withdrawn from the study for other reasons.

8.4 DOSE DELAYS/DOSE MODIFICATIONS

Patients should be assessed clinically for toxicity at each visit using the NCI CTCAE v4.0 (http://evs.nci.nih.gov/ftp1/CTCAE/CTCAE) grading scale. Dose delay and/or modification guidance is for adverse events considered at least possibly related to either ublituximab or ibrutinib. If cytopenias are deemed related to the underlying disease rather than study drug, dose modifications are not required, or are per investigator discretion.

A maximum four (4) week delay of treatment for recovery from toxicity is allowed to recover from hematologic toxicities to \leq Grade 3 or non-hematologic toxicities to \leq Grade 2 or to baseline level. If greater than a four (4) week delay is necessary, then the patient should discontinue treatment and continue to be followed for progression. If a patient withdraws consent or has documented progression, an end of study visit should be completed.

8.4.1 DOSE DELAY: UBLITUXIMAB

No reduction in the dose of ublituximab is permitted. Please refer to Section 8.2.1.1 and 8.2.1.2 for detailed information on infusion rate guidance for infusion related reactions related to ublituximab. Supportive care should be considered for any patient who experiences Grade \geq 2 cytopenias, or Grade \geq 1 non-hematologic toxicities. A maximum four (4) week delay for recovery from toxicity is allowed for both study drugs (individually or together) to allow recovery of hematologic toxicities to \leq Grade 3 or non-hematologic toxicities to \leq Grade 2 or to baseline level. If greater than a four (4) week delay is necessary for both study drugs, then the patient should discontinue treatment and continue to be followed for progression. If the patient withdraws consent or has documented progression, an end of study visit should be completed.

UTX-IB-301

If a patient in Arm A discontinues only one study drug (either ublituximab or ibrutinib), the patient may continue treatment with the other study drug per the protocol.

Grade 4 neutropenia or occurrence of neutropenic fever or infection: Delay ublituximab until Grade ≤ 3 and/or neutropenic fever or infection is resolved; consider growth-factor support as warranted; thereafter, resume at full dose. If delay is > 4 weeks, discontinue ublituximab. (If the underlying cause for the ANC reduction is considered to be disease related and is Grade ≤ 3 , treatment hold is at the discretion of the treating investigator).

Grade 4 thrombocytopenia: Delay ublituximab until Grade \leq 3; consider intervention with supportive care as warranted; thereafter resume at full dose. If delay is > 4 weeks, discontinue ublituximab.

Grade ≥3 non-hematological adverse event: Withhold ublituximab until Grade ≤2 at the discretion of the investigator; consider supportive care as warranted. Resume at full dose or if delay > 4 weeks, discontinue ublituximab.

8.4.2 DOSE DELAYS/MODIFICATIONS: IBRUTINIB

Interrupt ibrutinib therapy for any Grade 3 or greater non-hematological, Grade 3 or greater neutropenia with infection or fever, or Grade 4 hematological toxicities. Once the symptoms of the toxicity have resolved to Grade 1 or baseline (recovery), ibrutinib therapy may be reinitiated at the starting dose. If the toxicity reoccurs, reduce dose by one capsule (140 mg per day). A second reduction of dose by 140 mg may be considered as needed. If these toxicities persist or recur following two dose reductions, discontinue ibrutinib.

Once reduced, the dose of ibrutinib may not be re-escalated. If further evaluation of the toxicity reveals the event was not treatment related, this must be recorded in the medical record and dose re-escalation to the next higher dose level may be considered at the discretion of the investigator.

For adverse events related to ibrutinib, refer to Table 3: Study Drug Dose Reduction Levels: Ibrutinib provided below. Please refer to the FDA approved prescribing information for all safety updates and dose modifications for ibrutinib. For the most up to date information please see www.imbruvica.com.

TABLE 3: STUDY DRUG DOSE REDUCTION LEVELS: IBRUTINIB

Toxicity Occurrence	CLL Dose Modification After Recovery (Starting Dose = 420 mg)	
First	Restart at 420 mg daily	
Second	Restart at 280 mg daily	
Third	Restart at 140 mg daily	
Fourth	Discontinue ibrutinib	

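### Ibrutinib has two definitions of recovery: the delay rule in Protocol 8.4 and 8.4.1 is looser than the restart rule in 8.4.2, and nothing says which governs

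*Protocol*

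**What the plan says.** Four places in the Protocol bear on an ibrutinib hold.

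- **8.3** caps any delay for toxicity at four weeks and names no grade.
- **8.4** opens by covering events at least possibly related to either drug. It then says: "A maximum four (4) week delay of treatment for recovery from toxicity is allowed to recover from hematologic toxicities to" Grade 3 or lower, with non-hematologic toxicities to Grade 2 or lower, or to baseline. On exceeding the cap: "If greater than a four (4) week delay is necessary, then the patient should discontinue treatment and continue to be followed for progression".
- **8.4.1** is headed for ublituximab but widens the rule: "A maximum four (4) week delay for recovery from toxicity is allowed for both study drugs (individually or together"), with the same recovery grades. Its consequence is narrower: "If greater than a four (4) week delay is necessary for both study drugs, then the patient should discontinue treatment". It adds: "If a patient in Arm A discontinues only one study drug (either ublituximab or ibrutinib), the patient may continue treatment with the other study drug". Its ublituximab-only lines use matching grades: for neutropenia "Delay ublituximab until Grade ≤ 3 and/or neutropenic fever or infection is resolved", and for non-hematological events "Withhold ublituximab until Grade ≤2 at the discretion of the investigator".
- **8.4.2** holds ibrutinib for non-hematological events of Grade 3 or worse, for neutropenia of Grade 3 or worse accompanied by fever or infection, and for Grade 4 hematological events. It permits restart as follows: "Once the symptoms of the toxicity have resolved to Grade 1 or baseline (recovery), ibrutinib therapy may be reinitiated at the starting dose". Table 3, in the same section, sets the dose after recovery and gives 420 mg for a first occurrence. The section contains no time limit of its own and refers sites to the prescribing information.

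**The concern.** The same word, recovery, carries two meanings, and both reach ibrutinib. A site working from 8.4 or 8.4.1 can regard an ibrutinib toxicity as recovered while it is still non-hematologic Grade 2 or hematologic Grade 3. A site working from 8.4.2 must keep holding. With up to 200 sites (6.3), different practice is foreseeable.

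The stake is mainly patient safety and consistent exposure. The question arises in both arms, since both take daily ibrutinib; in Arm B, stopping ibrutinib ends all study treatment. A secondary stake is Protocol 12.1, which compares the number of ibrutinib dose reductions for toxicity between arms. Restart decisions made to different standards would add noise to that count.

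A related mismatch affects Arm A. Read alone, 8.4 stops treatment altogether after a delay beyond four weeks; 8.4.1 does so only when both drugs need the longer delay.

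**Working it through.** The plan gives no figure to reproduce here. The check is a comparison of the two rules.

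**Inputs**
- Recovered under 8.4 and 8.4.1: hematologic Grade 3 or lower, non-hematologic Grade 2 or lower, or baseline.
- May restart under 8.4.2: Grade 1 or baseline.
- Assumption: baseline Grade 0, so that the baseline alternative, which both rules contain, adds nothing.

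**Step 1. Compare the rules at each grade where a toxicity might settle.**

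| Toxicity settles at | 8.4 / 8.4.1 | 8.4.2 | Agree? |
|---|---|---|---|
| Non-hematologic 0 or 1 | recovered | may restart | yes |
| Non-hematologic 2 | recovered | may not restart | **no** |
| Non-hematologic 3 or worse | not recovered | may not restart | yes |
| Hematologic 0 or 1 | recovered | may restart | yes |
| Hematologic 2 | recovered | may not restart | **no** |
| Hematologic 3 | recovered | may not restart | **no** |
| Hematologic 4 | not recovered | may not restart | yes |

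The rules disagree at one non-hematologic grade (2) and two hematologic grades (2 and 3).

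**Step 2. Follow one patient.** A Grade 3 non-hematologic event leads to an ibrutinib hold and has improved to Grade 2 by week 4. Under 8.4 and 8.4.1 the patient has recovered within the cap. Under 8.4.2 the patient may not restart. No sentence says what happens next.

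**Step 3. Look at one hold trigger.** Grade 3 neutropenia with fever requires an ibrutinib hold under 8.4.2. The neutropenia itself already satisfies the hematologic level in 8.4 on the day the hold begins, so for that component the looser definition sets no recovery target.

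**Step 4. Ask where the looser grades come from.** They match the ublituximab-only lines in 8.4.1 (Grade 3 or lower for neutropenia, Grade 2 or lower for non-hematological events). A ublituximab rule extended to both drugs would explain the pattern. That is inference; the documents do not say so.

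**Step 5. Ask how far the Grade 0 assumption matters.** Section 5.1 admits patients with low counts (ANC from 750, platelets from 40,000). For a patient who enters with a cytopenia, return to baseline satisfies both rules, so the hematologic disagreement can shrink or vanish.

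**Step 6. Count patients.** This is not possible. The documents give no rate of toxicities that settle at the disputed grades, and the number treated differently is zero if every site follows 8.4.2.

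**The case against.** The best defense is that the sections do different jobs. Only 8.4.2 is worded as an ibrutinib restart rule; 8.4 and the general sentence in 8.4.1 set a maximum delay and what follows if it is exceeded. Table 3 applies after recovery, and 8.4.2 defines recovery as Grade 1 or baseline, so a site using Table 3 should be using the stricter grade. A specific rule would normally prevail over a general one, and 8.2.2 and 8.4.2 both point to the prescribing information.

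Much of this stands. A reader might infer that the protocol instructs sites to restart ibrutinib at 420 mg with Grade 2 or 3 toxicity present; it does not. The looser wording leaves room for that practice without directing it. A reader might also infer that the four-week cap has no stated grade. It has one: 8.4 and 8.4.1 name the grades in the cap sentence and allow baseline as well. Nor do the documents support an ibrutinib hold of unlimited length, because 8.3, 8.4 and 8.4.1 all cap delays and 8.4.2 need not repeat the cap.

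The defense does not remove the conflict. No text gives 8.4.2 or the label precedence over 8.4 and 8.4.1, and 8.4.1 is itself specific in naming both drugs singly. The label is not among the documents, so its effect cannot be judged. Even if the sections are read as a delay rule and a separate restart rule, the patient in Step 2 meets one and fails the other, with no stated disposition.

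On Arm A, 8.4.1 already lets a patient who stops one drug continue the other. What remains is that the discontinuation sentence in 8.4 lacks that limit.

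**Conclusion.** The point holds as an internal inconsistency in a safety instruction. Two definitions of recovery apply to ibrutinib, they differ at three grade levels when baseline is Grade 0, and the protocol does not rank them. Specific-over-general reading favors 8.4.2, but sites should not have to infer that.

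The effect on ORR is probably small. This is a judgment, since the number of patients affected cannot be derived.

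A reader might size the problem as a full four-week hold: 4 × 7 = 28 daily doses, 28 × 420 mg = 11,760 mg, or 28/112 = 25% of the doses in the 16 weeks (16 × 7 = 112) that SAP 3.5.1 requires as a minimum before the ORR analysis. That is the whole permitted hold. The difference between the rules is only the time from the looser grade to Grade 1 or baseline, which the documents do not give.

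A reader might also infer that a patient still above Grade 1 at week 4 must stop ibrutinib. The text does not settle this. Stopping or continuing the hold is a clinical trade-off, and in Arm B stopping would end all study treatment.

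**What to change.** Make three changes in the Protocol.

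1. In 8.4 and 8.4.1, limit the hematologic Grade 3 and non-hematologic Grade 2 recovery wording to ublituximab.
2. In the same places, state that ibrutinib restarts only at the 8.4.2 level, Grade 1 or baseline.
3. Align the discontinuation sentence in 8.4 with 8.4.1, so that in Arm A exceeding the permitted delay for one drug stops that drug only.

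Leave the ibrutinib hold triggers, Table 3 and the 12.1 comparison as they are. Whether a patient above Grade 1 at week 4 discontinues ibrutinib or stays on hold is for the sponsor to decide on clinical grounds and is not part of this change.

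The cost is two or three sentences by amendment, with IRB review under 14.2 because the rule bears on patient risk, and a notice to sites. No visits, tests or patients are added. The downside is that some patients stay on ibrutinib hold longer than the looser wording would have allowed.
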